9.1 Patient identification

Patients will be identified from the MDT lists from participating centres which will be screened weekly by local leads. Those satisfying inclusion and exclusion criteria will be approached to take part.

Additionally, for the patient interview qualitative component, local teams may mention the study to patients who have been previously treated with tongue base mucosectomy during their routine follow up appointments. The MOSES study team will not approach any of these patients directly. Adverts will also be places at peopleinresearch.org and at mosesstudy.co.uk for people to self-refer.

9.2 Consent

Once identified, eligible patients may be approached by the usual care team or research nurse either remotely or in person. No additional outpatient appointments or patient contacts should be required. Patients will be provided with copies of the **Patient Information Sheets (PIS)** and **Informed Consent Forms (ICF)**. Appropriate time will be given to patients to read and digest the information. Written consent will be taken by an appropriately trained member of the clinical team or a research nurse.

Re-consent

Following the implementation of protocol v4.1, patients who had already consented using ICFs prior to v3.0 may be re-approached, by an appropriately trained member of the local team, to re-consent to the study to be able to participate in the extended follow-up and molecular analyses.

Qualitative interviews

For the Qualitative Interviews, consent may be completed remotely by the patient and the MOSES team. As with face-to-face consent, the Patient Information Sheet should be provided, and the patient given adequate opportunity to ask questions about participation in the study. An electronic copy of the consent form will be stored in the Trial Master File by the Sponsor.

9.3 Functional outcomes and pain scores.

Patient will be asked to complete 10 sets of questionnaires: at baseline (pre-operatively); and post-operatively at 3 weeks, 6 weeks, 3 months, 6 months, 12 months, 24 months, 36 months, 48 months and 60 months. Patients will be asked to record their pain score at its worst, at its least and most of the time, on a Numeric Rating Scale. They will be asked to assess their swallow function by completing a M. D. Anderson Dysphagia Inventory (MDADI). Questionnaires may be completed in person, via post or

remotely (including telephone, video-call or electronic form) and returned to the MOSES team on the contact email provided.

9.4 Dataset and case report form (CRF)

The following fields will be recorded on the CRF (please see the MOSES CRF document for full list):

- Demographics
- Medical history
- Surgical history
- Investigations
- Peri-operative outcomes
- Conventional histology result
- Initial treatment plan
- Pain and swallowing function scores
- SSS histology result
- Oncological status, including disease recurrence and primary emergence
- Management of further disease
- Participation in clinical trial(s)

Data collected on the CRF can be used as source data.

9.5 Pseudonymisation

Each site will generate a unique study ID and use a 'key' to reference this to the NHS and hospital medical record number. This key will be stored locally at contributing trusts on an excel file on the hard drive of a secure NHS computer. The study key will be stored for the duration of the study and then destroyed in line with local processes for handling patient identifiable data. No patient identifiable data will leave the contributing trusts.

A case report form (CRF) will be created for each patient to record the above dataset including the unique study ID. This information will be shared with the central MOSES team via nhs.net mail to a central MOSES computer held at the Royal Marsden Hospital in the H&N office.

The central MOSES team will only receive and process pseudonymised data associated with the study ID. The central MOSES database will not record contributing sites by name so that individual cases are not linkable to their site of origin. The key to this information will be kept separately to the MOSES database.

Study ID will be formed from a three letter hospital code followed by a three digit consecutive number, e.g. RMH001, RMH002, etc.

9.6 Surgical technique

All centres known to be performing TBM in the UK will be invited to take part. The surgery will take part at the contributing centre adhering to their usual practices. This will encompass techniques using laser resection, endoscopically assisted techniques and resections using robotic systems. There is currently no standardised method for performing TBM. An affiliated project will look to generate a standard operating protocol (SOP) for TBM for potential future studies. The technique used in each case will be recorded on the CRF.

9.7 Handling of tissue specimens and histological processing

All tissue will undergo conventional histological processing at the local site and will be used to influence patient management by the local team according to local practices. The following tissues will then be requested to be sent by the local teams to RMH for further analysis:

- Oropharyngeal tissues from diagnostic surgeries attempting to identify the primary site (i.e., TBM specimens, and tonsils, if available)
- Cervical nodal specimens, from the diagnostic neck biopsies (fine needle aspiration cytology and/or core biopsies) and/or therapeutic neck surgeries, if available
- A buccal swab and/or blood sample (for germline DNA)

Where SSS is indicated (TBM and tonsil specimens, if available) the MOSES team will then send these tissues onto the RVI. Appropriate tissue handling practices will be observed. RMH uses FreezerPro Laboratory Management Software to facilitate handling and tracking of tissue specimens.

Anonymised histopathology reports will be requested from local centres. The macroscopic description will be used to orientate the submitted tissue blocks undergoing step serial sectioning.

Step serial sectioning

The paraffin blocks supplied from TBM and tonsil specimens will undergo step serial sectioning using the following method:

- Steps every 0.5mm with five serial 4 μ m sections taken.
- Each block will be processed in this way until the material is consumed.
- Slides will be stained with haematoxylin and eosin stain (H&E) and examined for signs of SCC.
- If an SCC is identified, then serial sections 2 and 4 will be submitted for HPV testing (p16 immunohistochemistry and high-risk HPV DNA in situ hybridisation).
- Serial sections 1 and 5 will be retained for repeat tests if required.
- The pathologist will compose a report and complete the relevant sections of the CRF.
- Unused material will be returned to the contributing centres if desired. Some material may be retained for further study, as detailed in the PIS and ICF.

Exploratory molecular analysis

Patients will be asked to provide buccal swabs and/or blood samples for germline DNA analysis. These samples may be provided at any time point following recruitment.

Packaging and sending

All MOSES blood and/or buccal swab samples should be collected, labelled, stored and shipped as detailed in the **MOSES Sample Collection Manual**.

The buccal swabs and/or blood samples will likely be obtained during a face-to-face contact as part of the patient's usual care pathway. In circumstances where samples cannot be obtained during a face-to-face contact, the local site team may send a **research pack** (supplied by the sponsor) to the participant, via post, containing the blood and buccal swab collection materials for those agreeing to re-consent. The pack will also contain the Cover Letter, PIS and ICF. The completed documents and sample collection materials may then be returned to the local site team using return labels, before being sent onto RMH as per the **MOSES Sample Collection Manual**.

All samples must be labelled with the participant's study identifier, date of birth and date of sample to enable cross-referencing. All samples should be sent by post to the following address:

[name] [name]
2S8
Chester Beatty Labs
The Institute of Cancer Research
[name]

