3.0	03/06/21	Clarification to recruitment target, amendment to inclusion/exclusion criteria
3.1	10/09/21	TBM Sample Recruitment period updated
4.1	01/10/21	Extend recruitment target, recruitment period, follow-up duration, and molecular analysis
4.2	18/03/22	Updated sample shipment details

2 Table of acronyms

Acronym	Meaning
CCR	Committee for clinical research
CH	Conventional histology
CRF	Case report form
CT	Computed tomography
CUP	Cancer of unknown primary
EBV	Epstein Barr virus
FNAC	Fine needle aspiration cytology
GCP	Good clinical practice
H&E	Haematoxylin and eosin stain
H&N	Head and neck
HNC	Head and neck cancer
HNSCCUP	Head and neck squamous cell carcinoma of unknown primary
HPV	Human papilloma virus
ICF	Informed consent form
IRAS	Integrated research application system
MDADI	M. D. Anderson Dysphagia Inventory
MDT	Multidisciplinary team
MRI	Magnetic resonance imaging
MTA	Material Transfer Agreement (Part of HRA Statement of Activities)
PET CT	Positron emission tomography and computed tomography
PIS	Participant information sheet
REC	Research ethics committee
RMH	Royal Marsden Hospital
RVI	Royal Victoria Infirmary, Newcastle (laboratories)
SAE	Stamped addressed envelope
SCC	Squamous cell carcinoma
SOP	Standard operating protocol
SSS	Step serial sectioning
TBM	Tongue base mucosectomy

3 Project summary

Study title	Evaluation of the role of tongue base MucOsectomy and Step serial Sectioning in the management of the unknown primary squamous cell cancer in the head and neck.
Short title	The MOSES Study.
Study design	Multicentre prospective observational cohort study, incorporating histopathological and molecular tissue analysis.
Study setting	UK centres performing TBM for suspected HNSCCUP.
Study participants	Patients with suspected head and neck squamous cell carcinoma of unknown primary (HNSCCUP) undergoing tongue base mucosectomy (TBM).
Planned sample size	100.
Follow-up duration	5 years.
Planned study period	Until recruitment of planned sample size.
Aim	To understand the current management of suspected HNSCCUP patients undergoing TBM in the UK, including adequacy of current histology, functional and oncological outcomes, and disease biology.

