Human papilloma virus (HPV) is thought to play a significant role in many of these cancers presenting as CUP.[6,7] Smaller or involved primary foci are known to be more common in HPV related cancers which may be contributing to the apparent incidence of these unknown primaries, or occultomas as they may also be called. A histological technique called step serial sectioning (SSS) allows examination of tissue specimens in greater detail than conventional histology. It has not previously been used to investigate the primary site in head and neck cancer but the oropharyngeal tissues that potentially harbour these small primaries make a sensible target to pioneer its usage. It is hypothesised that utilising SSS on tonsillectomy and TBM specimens may increase the identification rate of the primary site and may subsequently affect recommended management.

Currently, we do not understand why some cancers present with cervical metastases with no evident primary site. There has been an explosion in genomics research in many cancers, but this remains an understudied area in head and neck cancer. There are currently no treatments available to patients with head and neck cancer based on genomic insights. This study aims to begin to address the unmet need of patients who present with these poorly understood cancers and to provide a starting point for more detailed investigations into the relationships between cancer genomics and clinical outcomes.

6 Study aim and objectives

6.1 Aim:

To understand the current management of suspected HNSCCUP patients undergoing TBM in the UK, including adequacy of current histology, functional and oncological outcomes, and disease biology.

6.2 Primary objective:

- To establish if step serial sectioning (SSS), compared to conventional histology, improves identification of a primary site in TBM and tonsil specimens in suspected HNSCCUP.

6.3 Secondary objectives:

1. To compare the pick-up rate of primary cancers in TBM specimens between surgical methods (robotic vs laser vs endoscopic).
2. To prospectively evaluate swallowing function and pain scores after TBM.
3. To understand patient views and experiences of undergoing TBM for suspected HNSCCUP.
4. To report time-to-event data for local, regional and distant disease recurrence, and mortality.
5. To assess the molecular makeup of patients with suspected HNSCCUP undergoing TBM.

7 Study design and setting

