12.5 Safety Considerations

There are no immediate safety implications anticipated due to the observational and non-interventional nature of the study.

There is potential for primary cancers to be identified in some tissue specimens where it had been missed at the local site when undergoing conventional histology. These updated results from the pseudonymised specimens will not be available in a timeframe that could influence patient treatment.

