12.8 Expected Outcomes of the Study

TBM is a relatively new surgical procedure with little data relating to patients experience and recovery from this operation. The pain and MDADI questions will go some way to showing the acceptability of this procedure to patients. It is expected that by 6 weeks the pain and MDADI scores will have returned to near baseline. Most patients will go on to receive radiotherapy to their pharyngeal mucosa, which is known to worsen swallowing function. This data will go some way to clarifying that any subsequent difficulties may not be attributable to the TBM procedure.

Any increased pick up rate resulting from SSS could lead to wider adoption of this process in the management of HNSCCUP. The size of any primary sites identified through SSS over conventional histology will also be recorded and could influence the size of histological levels employed for future TBM and tonsillectomy specimens in the future management of HNSCCUP.

Data from the patient interviews and thematic analysis should help to guide patient goals for any further research in HNSCCUP. Of particular note will be the patients' wishes regarding timing of the tonsillectomy and TBM procedures, which can occur separately, particularly if initial investigation is performed in a peripheral hospital that does not offer TBM. The potential changes in management from identification of primary sites using SSS, and potential for escalation of treatment through the addition of concomitant chemotherapy will also be novel.

Results from the exploratory molecular analysis are expected to give us greater understanding of the molecular make-up of suspected HNSCCUP. Including, but not limited to, how cancers where the primary is identified differ from those primaries that remain occult, and how the cervical disease differs from primary site tissues in the oropharynx.

Results from this prospective observational study will form the foundation of a potential phase III trial investigating the roles of TBM and SSS in management of suspected HNSCCUP. The precise research question is yet to be established.

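### The planned CH and SSS rates describe what central SSS adds after local CH, but cannot by themselves credit that yield to step sectioning

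*Protocol*

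**What the plan says.** - **Objective (Protocol 6.2).** The contrast is between techniques: "To establish if step serial sectioning (SSS), compared to conventional histology, improves identification of a primary site in TBM and tonsil specimens in suspected HNSCCUP".
- **CH (9.7).** "All tissue will undergo conventional histological processing at the local site", with the result used by the local team under its own practices.
- **SSS (9.7).** The TBM and any tonsil blocks are collected at RMH, and "the MOSES team will then send these tissues onto the RVI". Of the material, 9.7 says "The paraffin blocks supplied from TBM and tonsil specimens will undergo step serial sectioning using the following method": a step every 0.5 mm with five serial sections at each step, until the block is used up. The pathologist then reports the result and fills in the relevant CRF sections.
- **Material requested (9.7).** Tissue and the local histopathology reports are requested. Nothing provides for the local CH slides to be re-read centrally, for SSS to be read locally, or for the central reader's finding at one ordinary level to be reported separately.
- **Endpoint and analysis (12.2, 12.4).** The endpoint is cancer found on histology, with no laboratory or reader named. CH and SSS pick-up rates are reported descriptively with 95% confidence intervals.
- **Use of the result (12.8).** "Any increased pick up rate resulting from SSS could lead to wider adoption of this process".

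**The concern.** Two things differ between a CH result and an SSS result: how finely the block was cut, and where, and in general by whom, the slides were cut and read. When a specimen is negative locally and positive at the RVI, the cancer may have been found because the steps reached tissue that CH did not sample. It may also have been found because another laboratory and pathologist looked again. The planned pair of rates gives one difference that contains both.

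This is separate from masking. A central pathologist who knew nothing of the local result would still be a second reader in a second laboratory.

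What is at stake is the attribution. Section 12.8 speaks of increased pick-up as the result of SSS and as a reason to adopt it more widely. If part of the gain comes from a second look, some of it might be had from central review of ordinary sections. The study as planned could not show whether that is so.

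**Working it through.** **1. The plan's own figures.** Section 12.1 gives a CH pick-up of 58%, an anticipated increase of around 10% (taken as percentage points, because it pairs 58% with 68%) and a target of 100. Its interval figures reproduce as the distance from the estimate to the upper exact (Clopper-Pearson) 95% limit: 12.60 for 35/60, 11.41 for 41/60, 9.80 for 58/100 and 8.98 for 68/100, against the stated 12.6, 11.4, 9.8 and 9.0. This point does not dispute them.

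**2. What varies between the two results.**

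| | CH | SSS |
|---|---|---|
| Laboratory | each contributing site | RVI |
| Reader | local | the reporting pathologist for SSS |
| Tissue | sections cut first | block left after CH |
| Cutting | local practice | steps every 0.5 mm until exhausted |

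No planned result holds laboratory and reader fixed while the cutting changes, so the CH–SSS difference cannot be divided from the two rates alone.

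**3. How large the non-stepping part could be.** Expected CH-negative patients per 100: 100 × (1 − 0.58) = 42. Let r be the share of these in whom a second laboratory or reader would find carcinoma without deeper stepping. The documents give no value for r, so it is assumed. The non-stepping part is 42r points, and what remains for stepping is 10 − 42r. This takes the 10 points to be CH-negative/SSS-positive cases, with no cases positive on CH and negative on SSS.

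| r (assumed) | 42r, points | Share of the 10 points | Left for stepping |
|---|---|---|---|
| 2% | 0.8 | 8% | 9.2 |
| 5% | 2.1 | 21% | 7.9 |
| 10% | 4.2 | 42% | 5.8 |

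The whole gain would be accounted for at r = 10/42 = 23.8%. That is the algebraic limit and not a prediction.

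**4. The confidence interval does not cover this.** For 10 gains in 100, the exact 95% interval is 4.9% to 17.6%. It reflects sampling error only and would be the same whatever r is.

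**5. What recording the step level adds.** At the RVI the same laboratory and reader see the first step level and all later ones. Comparing one level with all levels therefore holds both fixed. The first level is cut from tissue remaining after CH, so it stands in for a conventional section but is not the slide that the local pathologist read.

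**The case against.** The strongest defence is that routine local CH is the right comparator. The study is observational and descriptive, its aim includes the adequacy of histology as now practised, and it is meant to prepare a possible later trial. For that purpose, the yield of central SSS on top of routine CH is a legitimate quantity. This stands, and the rates should be kept. It does not reach the primary objective or 12.8, which are worded about the technique.

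It can also be said that the CRF is a separate document that may already capture the level, and that splitting a table is a matter for the SAP. The first is possible, and the fix allows for it. The second holds only if the level was recorded at reading: blocks are cut until nothing is left, so they cannot be re-cut later.

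Several stronger readings are tempting but not supported:

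- **That the protocol expects reading errors.** Section 12.5 foresees "primary cancers to be identified in some tissue specimens where it had been missed at the local site", but the sentence goes on to tie the miss to conventional histology. It does not separate a reading miss from a sectioning miss.
- **That only finds below the first level belong to SSS, and that this is conservative.** A first-level find may be a true gain from newly cut tissue, so the rule is too strict. In the other direction, a focus overlooked on the CH slide may be absent at the first level and reappear deeper, so deeper finds can still contain reader effect. The error runs both ways.
- **That the reader always differs.** This is likely but unstated. The protocol does not say whether the RVI's own trust contributes cases.
- **That a sizeable part of the gain is a reader effect.** The documents show the mechanism, not its size.

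**Conclusion.** The point holds as a limit on attribution. The planned rates validly describe the yield added by central SSS after routine local CH. They cannot by themselves show that step sectioning produced it, because laboratory and, in general, reader change at the same time. The size of that component is unknown. With r assumed between 2% and 10%, it would be 0.8 to 4.2 of the anticipated 10 points, given 58% CH pick-up, 100 patients and no CH-positive/SSS-negative cases.

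A reader might infer that the primary comparison is invalid or that the expected gain is spurious. The documents support neither. The change is still worth making, because it costs little and the information is best captured when the slides are read.

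**What to change.** **In 9.7**, unless the CRF already does so, record for each block the step level at which SCC is first seen. Use the diagnostic H&E section of each step, not serial sections 1 and 5, which 9.7 holds in reserve. Because 9.7 does not state outright which serial section is the diagnostic one, name it.

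**In 12.4**, report all CH-negative/SSS-positive cases as the gain of the central SSS pathway, split into:

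- (a) SCC already seen at the first step level, where a re-reading or re-cut difference cannot be excluded;
- (b) SCC seen only at a deeper step, which the same reader did not see at the first level.

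Present (b) as the part that needed stepping and (a)+(b) as the total, and do not attribute (a) firmly to either cause. For a patient with several blocks, count the case under (a) if any block is positive at its first level.

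**State the limit:** the first level is a proxy for a conventional section and not a re-read of the CH slide, so the split limits the reader effect but does not fully remove it.

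**Cost:** one CRF field, one table row, and possibly a smaller gain attributed to stepping. No new slides, tissue or reader are needed. The level of first detection would also serve the interest in 12.8 in how finely future specimens should be cut. A masked central re-read of the CH slides from CH-negative cases would measure the reader component more directly, but it costs more and is not needed for this change.

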10.1 Summary tables

The following tables summarises the time points at which respective data fields will be gathered and returned:

Procedure		Screening/ Day 0	3 wks.	6 wks.	3 mos.	6 mos.	12 mos.	24 mos.	36 mos.	48 mos.	60 mos.
Local team	Eligibility	x									
	Informed Consent	x									
	Medical and surgical history	x									
	Investigation results	x									
	Conventional histology result		x								
	CRF Completion	Page 1-2	Pages 3, 4, 5				Page 6	ICF v3.0 and above			
Patient/ Local team	Pain questionnaire	x	x	x	x	x	x	ICF v3.0 and above			
	MDADI questionnaire	x	x	x	x	x	x	ICF v3.0 and above			

Return of data		Screening/ Day 0	3 wks.	6 wks.	3 mos.	6 mos.	12 mos.	24 mos.	36 mos.	48 mos.	60 mos.
Local team to return CRF to RMH		x	x				x	ICF v3.0 and above			
Local team to return questionnaires to RMH		x	x	x	x	x	x	ICF v3.0 and above			
Local team obtain germline DNA samples (buccal swabs and/or blood samples)		Any time point									

in person or posted to patient	
Local team return tissues to RMH (TBM +/- tonsil specimens, cervical nodal specimens and buccal swab and/or blood samples)	Any time point

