12.1 Sample size

No a prior sample size calculation was performed as initial funding limited recruitment to analysis of 60 specimens to undergo SSS. Meta-analysis shows a pickup rate of 58% for this cohort. We anticipate a potential increase pick up rate of around 10%.

- With 60 specimens, the 95% confidence interval boundaries around the pickup rate are +/- 12.6% for 58% and +/-11.4% for 68%.

In anticipation of further funding, our sample size is increased to 100 to give greater confidence in the effect size.

- With 100 specimens, the 95% confidence interval boundaries around the pickup rate are +/- 9.8% for 58% and +/-9.0% for 68%.

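### Section 9.7 does not limit what the step-sectioning laboratory receives and nothing masks its pathologist to the conventional diagnosis, so the primary comparison is open to review bias

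*Protocol*

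**What the plan says.** The primary objective (Protocol section 6.2) is to establish whether SSS, "compared to conventional histology, improves identification of a primary site in TBM and tonsil specimens". Section 12.2 makes the endpoint the finding of cancer on histology, and section 12.4 reports the CH and SSS pick-up rates descriptively with 95% confidence intervals.

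Section 9.7 sets the order of work:

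- CH comes first: "All tissue will undergo conventional histological processing at the local site".
- The tissue then goes to the Royal Marsden (RMH), and where SSS is indicated "the MOSES team will then send these tissues onto the RVI", the Newcastle laboratory.
- On the local reports: "Anonymised histopathology reports will be requested from local centres. The macroscopic description will be used to orientate the submitted tissue blocks".
- On the SSS reading: "Slides will be stained with haematoxylin and eosin stain (H&E) and examined for signs of SCC".
- On recording: "The pathologist will compose a report and complete the relevant sections of the CRF".

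Sections 9.5 and 11 deal with pseudonymisation, which protects the patient's identity. Neither deals with what the SSS pathologist knows about the CH result.

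**The concern.** When the SSS slides are read, a CH diagnosis already exists for the same specimen and the central team has asked for the report. Requesting it is not a defect, because the study needs the CH result as comparator. The gap is that section 9.7 names a use for one part of the report without saying that only this part goes forward, and it sets no masking condition on the reading.

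Deciding whether a small focus on an H&E slide is carcinoma is a judgement, and the project summary (section 3) states that more primaries are expected on SSS. A reader who knows that CH was negative may look harder and over-call, which would raise the SSS rate, or may anchor on the negative result and under-call, which would lower it. A reader who knows that CH was positive may agree with it more readily.

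The difference between the two rates would then contain an effect of knowledge as well as of sectioning. Section 12.8 says that a higher pick-up rate from SSS could lead to its wider adoption and that the results will underpin a possible phase III trial, so the size of the difference matters even in a descriptive study.

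**Working it through.** **Is there a safeguard in the text?** Setting the provisions side by side:

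| Question | What the protocol provides |
|---|---|
| Does a CH result exist before SSS is read? | Yes; CH is done first (9.7) |
| Is the whole local report requested? | Reports are requested, with identity removed (9.7) |
| Is only the macroscopic part passed on? | Not stated; a use is given, not a limit (9.7) |
| Is the SSS reader masked, or SSS locked before disclosure? | Not stated (9.7, 9.5, 11, 12.4) |
| Does it say that the reader receives the CH diagnosis? | No |

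The route is therefore open, but it is not prescribed.

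**The protocol's own figures.** Section 12.1 gives a CH pick-up of 58% and adds: "We anticipate a potential increase pick up rate of around 10" per cent, that is 68%. Its four interval figures can be reproduced as the upper arms of exact (Clopper-Pearson) 95% intervals: 35/60 gives 12.60, 41/60 gives 11.41, 58/100 gives 9.80 and 68/100 gives 8.98, against the stated 12.6, 11.4, 9.8 and 9.0. The masking point does not depend on them. Only the 58%, 68% and 10 points are used below.

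**Scale of a possible bias.** The protocol gives no error rate. Every percentage applied below is an assumed excess, meaning calls made because CH is known, beyond what a masked reader would make. Zero is possible. Per 100 specimens:

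1. CH-negative specimens: 100 − 58 = 42.
2. Over-calling: 42 × 0.01 = 0.42 points for each 1% excess, and 42 × 0.05 = 2.1 points for each 5%. Over 2% to 10% this is 42 × 0.02 = 0.84 to 42 × 0.10 = 4.2 points.
3. If the 10-point gain is real, 100 − 68 = 32 remain negative, and each 5% excess adds 32 × 0.05 = 1.6 points.
4. Excess needed to create the whole anticipated gain with no true effect: 10 / 42 = 23.8%.
5. Anchoring on a negative CH: if 10% of 10 true SSS-only finds are missed, 10 × 0.10 = 1 point is lost.
6. Agreement with a positive CH: 58 × 0.05 = 2.9 points on the stand-alone SSS rate for each 5%, and nothing on the add-on yield (primaries found by SSS that CH missed).

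**The case against.** The strongest reply is that this argues from silence. Section 9.7 names a single use of the report, orientation of the blocks, and that points towards limited use. Nothing says that the microscopy or diagnosis travels to Newcastle. The case report form and any laboratory instructions are separate documents that may already mask the reader. All of this stands. It limits the point to an unguarded route, and it means that one sentence may settle the matter. It does not supply the safeguard: a stated use is not a restriction.

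A reader might infer that the SSS pathologist will in fact see the CH diagnosis. The protocol does not support that. A reader might also take the case report form as the route, since section 9.4 lists both results on it. But the summary tables in section 10.1 have the "Local team to return CRF to RMH", the pathologist completes only certain sections, and the layout is not available, so the form is not relied on here.

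Three further replies carry some weight:

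- An SCC found on SSS leads to p16 and HPV testing on adjacent sections, and section 12.8 records the size of SSS-only primaries. These leave a trail that could expose over-calling. Neither is stated to be confirmatory, and neither checks a negative reading.
- A reading already made cannot be masked by an analysis plan, but a masked re-read by another pathologist might be possible if the slides are kept. Section 9.7 retains some sections and does not say how long the H&E slides are held.
- Masking would not remove the change of laboratory and reader between CH and SSS. That is a separate matter, and the protocol does not claim that the difference is due to sectioning alone. It is no reason to leave open a source of bias that is easily closed.

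**Conclusion.** The point holds as a gap in the conduct of the primary comparison: the plan as written permits an unmasked SSS reading and contains no visible safeguard. It does not hold as a claim that the reading is unmasked, or that the results are biased.

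Size and direction cannot be fixed from the protocol. On assumed excess rates, each 5% of over-called CH-negatives moves the SSS rate by 2.1 points, or 1.6 if the expected gain is real. That is enough to distort an anticipated gain of about 10 points. A reader might go further and infer that review bias could manufacture the whole gain. That would need an excess of about 24% of CH-negatives, which is unlikely. The agreement effect of 2.9 points touches only the stand-alone SSS rate.

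This is a cheap improvement worth making. It rests on the protocol as available, without the case report form or laboratory procedures.

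**What to change.** Add to section 9.7:

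- The central team releases only the macroscopic description and the block key to the SSS laboratory, with the microscopy and diagnosis held back.
- The SSS result is recorded and locked before the CH diagnosis is disclosed to the SSS pathologist.
- Any blocks known to have been read with the CH result available are reported as such. Past readings need not be reconstructed.

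If another study document already masks the reader, a sentence in 9.7 saying so is sufficient.

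The cost is slight administrative work for a team that already forwards the tissue: extracting the text and holding back the diagnosis until the lock. No extra reader, procedure or specimen is needed, and the sample size is unchanged. Care is unaffected, because SSS results are not fed back to the treating teams (sections 12.5 and 12.6).
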